5.7 Withdrawal of Subjects

We do not anticipate a need to withdraw a participant from the research entirely. If a participant becomes pregnant, we become aware of a serious physical or mental health issue, or the participant's primary care provider notifies us that the individual should not continue the intervention, the participant will cease participation in the intervention activities of the research; however we will continue to follow the individual through completion of the study via CDW and self-report.

If a participant chooses to withdraw him/herself from the research, we will confirm with the individual that we may continue to follow him/her in CDW. If the individual declines, we will respect his/her choice and not collect additional data from CDW; however we will use any data collected up to the date of withdrawal.

For the purposes of follow-up, we will consider an individual "lost to follow up" if we are unable to collect either primary 12-month endpoint.

6.0 Reporting

6.1 Quality monitoring

The investigators will closely monitor and prepare annual summary reports on:

- Patient accrual and follow-up completion/retention in relation to goals and timeline.
- Randomization process and group comparability on the balancing variables.
- Key baseline characteristics of the sample, by blinded group, on the primary and secondary outcome variables.
- Intervention adherence.
- Protocol violations.

6.2 Data Safety and Monitoring Board.

This study will be reviewed regularly (at least annually) by a DSMB convened by the national director of VA HSR&D. This board will monitor the quality of data, progress of recruitment, as well as the incidence of adverse events between arms.

6.3.1. Adverse event monitoring.

To ensure unbiased determination across treatment arms, at 12- and 21-month follow-up contact we will ask participants to complete a survey about potential adverse events (AE), serious adverse events (SAE) and unanticipated problems (UP) employing a body system-based assessment. We define SAEs as those requiring hospitalization or death.

Study staff will collect adverse events using participant self-reports collected at 12 and 21 months. Study staff will also perform chart reviews looking for discharge summaries for the 12 month time period. Study staff will later complete additional chart reviews looking for discharge

summaries for the 21 month time period among patients who do not complete 21 month surveys. [name] or another clinician will assess each AE for duration (start and stop dates and times), expectedness in the study population, severity, outcome, treatment, and relation to study activity.

To account for potential differential survey response rates by arm, we will also query the electronic medical record and compile hospital admissions from randomization through 24 months post randomization. We will report the number of hospitalizations by arm to in our final DSMB report.

The following are expected adverse events in the POWER population of participants who have obstructive sleep apnea, a high BMI, and adopt healthy eating and physical activity program:

- Gastrointestinal symptoms related to change in diet.
- Musculoskeletal symptoms or injury resulting from increased physical activity, including increasing symptoms such as chest discomfort, shortness of breath, and leg cramping.
- Development of weight and OSA associated medical disorders including diabetes, hypertension, liver disease, cardiovascular disease, cerebrovascular disease, arrhythmias, asthma, COPD, clotting problems, and other lung related conditions;
- Development or exacerbation of mental health conditions, the worsening of which is known to be associated with poor sleep, including depression, anxiety, posttraumatic stress disorder, and bipolar disorder.
- Development or exacerbation of eating disorders including binge eating disorder, anorexia nervosa, and bulimia nervosa.
- Development of other conditions associated with unhealthy health behaviors, such as from tobacco and alcohol disorders (e.g., cancer).
- Age related illnesses, such as pneumonia, urinary tract, and skin infections.
- Motor vehicle collision or other accidents arising from excessive sleepiness.
- Death

Upon discovering an unexpected and related SAE, study staff will provide the IRB and DSMB with a report describing the duration (start and stop dates and times), severity, outcome, treatment, and relation to study activity, according to the required timelines. The DSMB may request additional information if it deems additional deliberation is warranted.

For all other events, staff will summarize and report to the DSMB on an annual basis the numbers and types of all AEs by unidentified treatment arms. At their discretion, the DSMB may request unblinded results to determine the nature and extent of effect of the intervention. Should the DSMB make this request, we will maintain blinding of the investigators and the staff involved in follow-up data collection and analysis. If, at any time, the investigators believe they are seeing an unexpected increase in SAEs that is a cause of concern, they will bring this to the attention of the DSMB.

For annual reporting, staff also will provide the quality monitoring report to the DSMB.

At the annual meeting, the DSMB will review AE/SAEs and the quality of data, as well as review study progress and provide objective recommendations, as appropriate, with respect to:

- Determination of any actions to be taken in response to SAEs.
- Reports related to study operations and the quality of the data.
- Consideration of early termination of the study because of treatment safety concerns or inadequate performance.
- Modifications in the study protocol concerning recruitment, participant retention, data quality, outcome assessment, statistical analysis, or general trial operations.

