5.5 Study Evaluations

- Clarified timeline of compensation, in alignment with approved information statement.

5.5.1 Primary Outcomes:

- Clarified weight collection to align with outcomes currently registered with clinicaltrials.gov. The co-primary outcome of weight will include clinically measured weights identified from CDW. We originally planned to include self collected weights collected as a contingency. However, given the trajectory of the COVID-19 pandemic and clinic availability, we made the decision to only use clinical weights, and explore self-weights in secondary analyses. Should clinical weight availability change as we enter primary outcome collection period, we may revisit this decision.
- Also clarified that self-weights are not measured at baseline, but shortly following randomization when intervention scales are sent.
- Updated Table 5 to align with changes above.

5.5.1 Secondary Outcomes:

- Added descriptions of self-reported nightly sleep apnea treatment adherence and sleep duration at baseline, 3, 12, and 24 months. These are currently being collected in IRB approved forms.
- Updated Table 5 to align. Also added reports of intervention participant self-monitoring and intervention adherence at 3 and 12 months which is documented in 5.3.6.4.

5.5.4. Monitoring for eating disorders:

- Added additional question to 3-month surveys about the development of eating disorders.

5.5.5 Physiologic OSA Severity:

- Added details around pre-test screening and practices.
- Clarified that we will conducting sleep studies among up to 200 participants per arm.

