6.3 Adverse event monitoring

- Added a comparison of hospitalization rate between arms through 24 months using data compiled from the CDW.

Abstract

1. Objective(s) and Hypotheses:

Our primary aim is to test the effectiveness of a proactively delivered and pragmatic weight loss intervention to improve co-primary endpoints of sleep-related quality of life and weight among Veterans with obstructive sleep apnea (OSA) and obesity. Secondarily, we will compare additional outcomes between groups: cardiovascular risk scores, sleep symptoms, and AHI. Finally, we will also conduct an implementation process evaluation informed by the RE-AIM framework to identify predictors and determinants of population uptake of the intervention, alternative guideline-based treatments for OSA and obesity, and the achievement of patient-centered outcomes.

2. Research Design:

We plan a hybrid type 1 pragmatic randomized controlled trial assessing effectiveness and an implementation process evaluation.

3. Methodology

We will proactively identify Veterans with OSA and obesity nationwide using data from the CDW (n=696), randomizing patients 1:1 to usual care plus the GLB weight loss intervention or usual care alone. We will collect primary outcomes at 12 months, but we will also collect outcomes at 3 and up to 24 months to assess trends over time. We will use quantitative and qualitative methods to assess determinants of implementation of our intervention and other guideline-based treatments for OSA and obesity, budget impact, and maintenance of patient-centered outcomes.

4. Findings/Progress to Date:

Recruitment began on 4/4/2022, analysis has not begun. No interim analysis planned.

5. Relevance to VA Mission

Our research tests a program of proactively providing Veterans with OSA the tools to manage weight loss in a way that is independent of local provider time and resources. Our research addresses a key gap in Veteran's health in a way that aligns with important VA priorities including population health, virtual care, access, and health care value. We anticipate our intervention can efficiently achieve improvements in quality of life while reducing the burden and risk of serious comorbidities.

List of Abbreviations

- Adverse event (AE)
- American Heart Association (AHA)
- Body mass index (BMI)
- Cardiovascular disease (CVD)
- Centers for Disease Control and Prevention (CDC)
- Centers for Medicare and Medicaid Services (CMS)
- Chronic obstructive Pulmonary Disease (COPD)

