5.2 Recruitment Methods

5.2.1 Enroll Veterans nationwide with OSA and obesity

5.2.2 Identify eligible participants through CDW:

We apply CDW algorithms to identify potentially eligible participants and verify eligibility via chart review using approved platforms including JLV/CAPRI (see Table 4, Section 5.4).

5.2.3 Screening for index weight/BMI:

Using CDW, we will identify Veterans with prior sleep study (CPT 95800, 95801, 95806, 95810, 95811), with associated diagnosis of OSA, an eligible BMI (index weight), a weight measurement indicating obesity (to minimize spurious inclusion), and who are likely free of exclusionary conditions searchable in CDW. We will retain pertinent socio-economic, demographic, and healthcare utilization data on all individuals identified to inform our organizational partners about the potential reach of the program.

5.2.4 Oversampling:

We may oversample:

- Women – our goal is to enroll approximately 30% of the cohort being female;
 - As we approached a third of our randomization goal, we observed that approximately 25% of enrollees were female. In order to increase our target oversampling, we may evaluate and re-mail an invitation to women. Our criteria include female non-responders who had an initial mailing at least 2 weeks prior and have an end of window greater than 2 weeks away.
- Minorities, if necessary, to have a balanced proportion of the cohort

5.2.5 Research invitation:

Using patients identified through CDW, we will mail and/or email invitations to enough Veterans to enroll 696 subjects. The invitation will contain:

- Flyer;
- Invitation Letter;
- Information Sheet;
- Opt in/out Post Card;
- Email decryption instructions;

We may pursue the option of posting the packet on the HSR&D public website for easy access in the future.

In order to meet our target recruitment timeline, we may re-mail and/or re-email to non-responders if they have not replied two weeks or more after initial mailing/emailing.

Once we meet our randomization goal, we will inform participants who have opted-in but are not yet randomized that enrollment is closed.

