- Inability to speak, read, or understand English
- Recent or active weight loss interventions including prescription weight-loss medications in last 90 days, participation in group or individual weight loss programs led by trained personnel in the past 90 days, and prior bariatric surgery or plans for bariatric surgery during the study period.
- Expected weight loss because of alternate explanations such as from illness
- High variability in weight due to fluctuations in volume status (e.g., ascites - liver disease, chronic heart failure)
- Safety and/or adherence concerns due to severe physical or mental health issues or life expectancy < 24 months. For example:
 - o 1) Outpatient health encounter within the last year for malignancy, chronic respiratory failure, schizophrenia, psychosis, dementia, substance use disorders, anorexia, bulimia, binge eating disorder
 - o 2) Hospitalization in the last 6 months
 - o 3) Receiving hospice or palliative care.
- Pregnant or planning to become pregnant during the study period
- Participation in other intervention studies

Phone Screening prior to randomization: To further ensure identification of exclusions (Table 4), study staff conduct a brief phone screening questionnaire during recruitment. Included in this screening, as of February 2023, will be a series of questions aimed at identification of eating disorders. Should a potential eating disorder be identified, the Veteran will not be enrolled in the study.

Non-Veteran Eligibility Criteria: As described in 5.2.6. We will approach all study staff employed as lifestyle coaches for qualitative interviews.

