Secondary Patient Reported Outcomes: Sleep Symptoms (Sleep-Related Disturbance and Impairment): We will assess sleep symptoms using the 8-item sleep disturbance and sleep-related impairment scales from the NIH PROMIS set.⁷¹ [name] validated these instruments to assess responsiveness to OSA treatment, and found greater responsiveness for PROMIS relative to the standard Epworth sleepiness scale.⁷² Together, these measures address the spectrum of sleep symptoms caused by OSA.⁷³ Global impression of change: We will also have subjects rate their change in symptoms using the single-item patients' global impression of change (PGI-C). PGI-C has been validated in the context of OSA treatment and asks patients to rate their global change in symptoms on a 7 point scale from "1-Very Much Improved" to "7-Very Much Worse".⁷⁴ Well-being: We will use a 3-item survey designed to assess Veterans' well-being which assesses overall life satisfaction as well as their ability to be regularly involved and participating in activities that they find important.

5.5.4. Monitoring for eating disorders: In addition to the outcomes outlined above, we will ask participants at 3-month surveys if they have developed symptoms consistent with eating disorders, using Veteran-centric language already in use by VA (<https://www.womenshealth.va.gov/WOMENSHEALTH/topics/disordered-eating.asp>). If participants indicate that they have developed new symptoms, we will contact them by telephone to confirm their selection. If confirmed, we will encourage them to discontinue any active lifestyle interventions focused on weight loss, and encourage them to discuss these symptoms with their primary care provider. If we are unable to reach participants indicating eating disorder concerns within 1 week, we will send them a letter summarizing the above information.

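### Apart from one eating-disorder item at month 3, adverse events without admission are first solicited at month 12, so resolved events from the months 1–3 ramp-up rest on 9–12 months' recall

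*Protocol*

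**What the plan says.** **Solicited events.** Protocol 6.3.1: "at 12- and 21-month follow-up contact we will ask participants to complete a survey about potential adverse events". The survey goes through body systems, and staff collect adverse events from these two self-reports. SAP section 10 gives the same two time points.

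**Other sources.** Protocol 6.3.1 adds chart review for discharge summaries and a record query for hospital admissions up to 24 months. SAP section 10 also limits its scheduled chart search to discharge summaries. It does have the assessing clinician use the chart alongside self-report once an event is known, and start and stop dates are part of that assessment.

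**Before month 12.** Protocol 5.5.4: "we will ask participants at 3-month surveys if they have developed symptoms consistent with eating disorders". If a telephone call confirms the answer, "we will encourage them to discontinue any active lifestyle interventions focused on weight loss", and the participant is urged to see primary care. The log for version 2.8 (02/22/2023) records the origin of the item: "Added additional question to 3-month surveys about the development of eating disorders". The Protocol abstract states: "Recruitment began on 4/4/2022, analysis has not begun".

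**Exposure and expected harms.** The 12-session curriculum is delivered in the first three months, with walking built up to 150 minutes a week by its end (Protocol 5.3.6.1 and 5.3.6.2). The expected events in 6.3.1 include gastrointestinal symptoms from the diet change, musculoskeletal symptoms or injury from the activity, and "Development or exacerbation of eating disorders including binge eating disorder, anorexia nervosa, and bulimia nervosa".

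**Existing contact.** Both arms already receive a month-3 survey (Protocol 5.5.1 and Table 5; SAP section 3). No adverse-event items other than the eating-disorder question are described for it. The survey forms themselves are not in the documents.

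**The concern.** The harms most closely tied to the intervention are expected while diet and activity are being changed, and the plan does not ask about them until the intervention year is over. A strained knee or some weeks of stomach upset in month 2 that has settled may be forgotten or misdated by month 12. Participants are told their arm (Protocol 5.3.3), so recall need not fail equally in the two groups. Coaches are in regular contact with the intervention arm only, so unsolicited reports may also be unequal.

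Two things are at stake. One is the by-arm account of non-serious events, which a reader could take as evidence of safety when wider VA rollout is considered. The other is the annual DSMB review, which has no solicited non-serious data from a participant's first year except the eating-disorder item.

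**Working it through.** **1. What each source can capture**

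| Source | When | Finds events without admission? |
|---|---|---|
| Body-system survey (Protocol 6.3.1; SAP 10) | Months 12 and 21 | Yes, by recall |
| Discharge-summary review (Protocol 6.3.1; SAP 10) | Months 12 and 21 | No |
| Admission query (Protocol 6.3.1) | 0–24 months | No |
| Eating-disorder item (Protocol 5.5.4) | Month 3 | That condition only |
| Coach reminders every other week (Protocol 5.3.6.2) | Intervention arm only | No safety question described |
| Stopping rule (Protocol 5.7) | Any time | Only if staff learn of a serious issue or the provider reports one |

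**2. Recall interval.** The documents state no such figure to reproduce. Recall is the survey month minus the onset month.

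- Onset in months 0–3, asked at month 12: 12 − 3 = 9 to 12 − 0 = 12 months. The mean is 12 − 1.5 = 10.5 if onset is uniform (assumption).
- Onset in months 0–3, asked at month 3: 0 to 3 months, mean 1.5.
- No window is given for the survey. If it were the 9–15 months used for clinical weight (assumption), the range would be 9 − 3 = 6 to 15 − 0 = 15 months.

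This applies to resolved events. One still present at month 12 can be reported as current.

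**3. Who was asked the month-3 eating-disorder item.** The item dates from 02/22/2023. A participant whose month-3 date fell earlier was randomized before 11/22/2022, which is day 232 after 4/4/2022. I use the 2022 start because version 2.10 of the Protocol (5/16/23) says that 12-month outcomes were then being collected.

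- Uniform recruitment over 12 months (Protocol 5.5.6.3 speaks of a year): 232/365 = 64%, or about 442 of 696.
- Uniform recruitment over 24 months (assumption): 232/730 = 32%, or about 221 of 696.

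The range is therefore roughly a third to two thirds. The eating-disorder questions at entry are equally recent: "Included in this screening, as of February 2023, will be a series of questions aimed at identification of eating disorders".

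**4. Whether month-3 contacts are still open at 03/04/2025.** Protocol 5.2.4 remarks: "As we approached a third of our randomization goal, we observed that approximately 25% of enrollees were female". The log places that text at version 2.6, 08/24/22, day 142. Reading it as 30–33.3% of the target, 696 is reached at day 142/0.333 = 426 to 142/0.30 = 473, that is June–July 2023. The last month-3 date is then September–October 2023. With 24 months of recruitment (assumption) it is July 2024. A contact would still be open only if someone had been randomized after about 12/04/2024, 32 months after recruitment began.

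**The case against.** The best defence is that this is a pragmatic trial of care that SAP section 5 describes as guideline-consistent. Survey timing is the same in both arms, and no formal test of non-serious events is planned. The DSMB receives counts by unidentified arm. Providers are contacted before randomization (Protocol 5.3.2), recent eating-disorder encounters are excluded (5.4), and coaches log the purpose of contacts (5.5.6.3). Under SAP section 10 the chart can help date events that reached medical attention. A longer month-3 form could also cost some completion.

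Most of this stands, and it keeps the point minor. It does not remove the gap, because none of these safeguards is described as soliciting non-admitted events in the first year. Equal timing makes the interval equal, but not the recall of people who know their arm.

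Four stronger readings are tempting, and the documents do not support them.

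- A reader might infer that serious harm goes undetected. Admissions have two searches of their own. Deaths are not a matter of participant recall.
- A reader might infer that eating disorders starting after month 3 go unrecorded, or that the stopping advice is then useless. They are a listed expected event and can be reported at month 12. Advice to stop active weight-loss efforts and see primary care still has use then, since self-monitoring is encouraged beyond the 3-month core. No scheduled question falls between months 3 and 12, but an eating-disorder item at month 12 would not close that interval.
- A reader might project the early accrual pace to a single share not asked the month-3 item. The accrual remark is approximate, its amendment date need not be the date of observation, and the lag from opening recruitment to first randomization is not given. Only the wide range is supported.
- A reader might infer that the bias favours the intervention. Forgetting could hide intervention-related events, but coach contact could bring more of them to light. The direction is open.

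**Conclusion.** The point holds, at minor severity. For resolved, non-admitted events of the ramp-up, the plan relies on 9 to 12 months' recall where an existing contact would allow 0 to 3. This rests on the survey content as the documents describe it; a month-3 form that already carried adverse-event items would answer it. No event rates are given, so the number missed cannot be estimated. The primary analysis and admissions are unaffected. The share not asked the month-3 eating-disorder item is substantial but uncertain, and depends on how recruitment was spread over time and on how quickly the new form came into use.

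**What to change.** **Design change.** In Protocol 6.3.1 and SAP section 10, add the existing body-system adverse-event items to the month-3 survey in both arms. Keep ascertainment on the surveys rather than through coaches, whom only one arm has. The cost is a slightly longer form, with a small risk to completion, and more reports for the clinician to review.

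**For participants already past month 3, which at the current version is almost certainly all of them.** Missing month-3 answers cannot be recovered, so what remains is reporting from data already held:

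- non-serious events by arm and survey period (month 12, month 21), with the number of respondents per arm;
- by arm, the number actually asked the month-3 eating-disorder item, so that a low count is not read against all 696;
- a statement of the recall limit beside every comparison of non-serious events, noting where chart review helped to date an event.
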